7.2.3 Other safety-related reports

As Sponsor, MEDSIR will assess constantly the benefit/risk rate of the trial, that means a continuous evaluation of the safety profile of the drugs under investigation will be done using all available information. MEDSIR will provide the regulatory agencies and competent authorities and the investigators with any relevant information that may affect the benefit/risk rate of the trial. An annual Development Safety Update Report (DSUR safety report) for IMP will be prepared and distributed by MEDSIR or its designee in accordance with all regulatory reporting obligations and local regulatory requirements.

In order to ensure the correct and necessary exchange of safety related information between MEDSIR (as Sponsor) and Roche (as the owner of the IMP), a project specific Safety Data Exchange Agreement will be established and signed between both companies.

MEDSIR or its designee will report any finding of noncompliance (as failure to follow any applicable regulation or institutional policies that govern human subjects' research) and/or serious noncompliance (as noncompliance that materially increases risks that result in substantial harm to subjects or others, or that materially compromises the rights or welfare of participants) according to any reporting obligation and local regulatory requirements.

7.2.4 Pregnancy reporting

Irrespective of the treatment received by the subject/patient, any subject/patient's or subject/patient's partner pregnancy occurring during study treatment or within 10 days after the

last dose of study treatment (for patients taking giredestrant) or 60 days following cessation of therapy (for patients in the tamoxifen arm) must be reported within 24 hours of investigator's knowledge of the event.

Patients will be instructed to immediately inform the investigator if they become pregnant during the study or within 28 days after the final dose of study drug.

Pregnancies will be treated as SAEs and the investigator will complete a Clinical Trial Pregnancy Reporting Form and forward it to the Sponsor according to the reporting instructions provided by MEDSIR at the site initiation visit and filed in the Investigator's File. The investigator should discontinue study drug and counsel the patient, discussing the risks of the pregnancy and the possible effects on the fetus. Monitoring of the patient should continue until conclusion of the pregnancy. Any serious adverse events associated with the pregnancy (e.g., an event in the fetus, an event in the mother during or after the pregnancy, or a congenital anomaly/birth defect in the child) should be reported on the Adverse Event eCRF.

The subject/patient will be asked to provide follow-up information on the outcome of the pregnancy, including premature termination should the case arise and on the infant until 12 months of life. Spontaneous miscarriage and congenital abnormalities will also be reported as SAEs. Follow-up queries may be sent, asking for further information, if required for a comprehensive assessment of the case.

The follow-up period will be deemed to have ended when the health status of the child has been determined at 12 months of the infant's life.

Additional follow-up information on any IMP -exposed pregnancy and infant will be requested at specific time points (i.e., after having received the initial report, at the end of the second trimester, two weeks after the expected date of delivery, and at 3, 6, and 12 months of the infant's life).

A spontaneous abortion should be classified as a serious adverse event (as the Sponsor considers abortions to be medically significant), recorded on the Adverse Event eCRF, and reported to the Sponsor immediately (i.e., no more than 24 hours after learning of the event).

If a therapeutic or elective abortion was performed because of an underlying maternal or embryofetal toxicity, the toxicity should be classified as a serious adverse event, recorded on the Adverse Event eCRF, and reported to the Sponsor immediately (i.e., no more than 24 hours after learning of the event). A therapeutic or elective abortion performed for reasons other than an underlying maternal or embryofetal toxicity is not considered an adverse event.

All abortions should be reported as pregnancy outcomes on the paper Clinical Trial Pregnancy Reporting Form.

Any congenital anomaly/birth defect in a child born to a female patient exposed to study drug should be classified as a serious adverse event, recorded on the Adverse Event eCRF, and reported to the Sponsor immediately (i.e., no more than 24 hours after learning of the event).

8 STATISTICAL CONSIDERATIONS

8.1 Sample size

A total of 92 patients will be enrolled in this trial and randomized 1:1 in the arm A with giredestrant (GDC-9545) (n=46) and the arm B with tamoxifen (n=46), with an expected accrual time of approximately 16 months and an additional 0.5 months for follow-up from end of accrual until EoT. EoS will be 28 days (+/- 3 days) after last dose of study treatment is taken.

8.2 Sample size

The analysis will compare absolute changes for Ki67 expression between baseline score and the evaluation after the treatment. The sample size was based on a superiority contrast between two study arms analyzed with a two-sided t-test set at 0.05 alpha level. We assumed a 70% mean in giredestrant (GDC-9545) Arm vs. 50% mean in tamoxifen with a 29% common standard deviation, according to the results observed (Dowsett, Smith, et al., 2005). We planned 34 patients per arm to attain an 80% power.

The final analysis will be conducted with unpaired Wilcoxon test because of the non-asymptotic distribution of data. We assumed that asymptotic efficiency of Wilcoxon test relative to the t-test, never falls below 0.86 (Jr & Lehmann, 1956). In addition, we expect a 10% dropout rate. So, 46 patients per arm will be finally recruited. We used the R software version 4.0.2. released on 2020-06-22 ("pwr").

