1.4 Rationale for Ki67 biomarker as primary endpoint

There has been a huge effort to find surrogate markers that can select a good prognosis population in patients treated with NET. Because anti-estrogen therapy mainly induces cell-cycle arrest, markers of tumor cell proliferation have been used to measure the *in situ* action of these drugs. In this scenario, Ki67 has emerged as a biomarker of efficacy after neoadjuvant treatment of luminal breast cancer. Ki67 is a nuclear antigen expressed by all proliferating cells between the late G1 and M phases of the cell cycle (Scholzen & Gerdes, 2000). There are three main studies showing that a lower Ki67 score in response to NET results in better long-term disease-free recurrence outcomes, while high Ki67 levels predicts worse prognosis (Guerrero-Zotano & Arteaga, 2017).

The IMPACT trial demonstrated that 2 and 12 weeks of neoadjuvant treatment with anastrozole significantly decreases Ki67 expression (76% and 82%, respectively) compared to tamoxifen alone (59% and 62%, respectively) or the combination of anastrozole plus tamoxifen (64% and 61%, respectively), and was correlated with an increased recurrence-free survival. However, there were no significant differences in overall response. (Dowsett, Smith, et al., 2005; I. E. Smith et al., 2005).

In the P024 study, 16 weeks of neoadjuvant treatment with letrozole achieved a greater overall response rate (ORR) compared to tamoxifen (55% vs. 36%, respectively) and a significant reduction of Ki67 (87% vs. 75%, respectively) (Ellis & Ma, 2007).

The ACOSOG Z1031 trial compared the efficacy of neoadjuvant exemestane, letrozole or anastrozole treatment for 16 to 18 weeks and shown that all three AIs produced an equivalent rate of Ki67 suppression, preoperative endocrine prognostic index (PEPI) score and there were no differences in surgical outcome (Ellis et al., 2011).

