The phase II coopERA trial (NCT04436744) was a two arm, open-label, multicenter trial aimed at evaluating the efficacy, safety and pharmacokinetics of giredestrant (GDC-9545) plus palbociclib compared with anastrozole plus palbociclib in postmenopausal women with untreated ER-positive/HER2-negative EBC. 221 patients with baseline Ki67 score $\geq 5\%$ were randomized 1:1 to receive 14 days of anastrozole (1 mg, PO QD) or giredestrant (GDC-9545) (30 mg, PO QD) (window-of-opportunity phase, WoO) followed by 16 weeks (four 28-days cycles) of additional neoadjuvant palbociclib (125 mg, PO, D1-21) treatment prior to surgery. The primary objective of the study was to measure tumoral Ki67 changed between baseline and post-WoO samples. In ESMO Breast 2021, preliminary results were shown for 83/202 planned patients. Two-week relative Ki67 reduction was significantly greater with giredestrant (GDC-9545) than anastrozole (80% versus 67%, respectively) and a consistent Ki67 suppression was observed in patients with baseline Ki67 $\geq 20\%$ (giredestrant (GDC-9545): 83% reduction; anastrozole: 71%) or $< 20\%$ (65% vs 24%). After 14 days of treatment, 25% of tumors exhibited complete cell cycle arrest (secondary objective) with giredestrant (GDC-9545) versus 5% with anastrozole. Patients treated with giredestrant (GDC-9545) had fewer AEs than anastrozole.

Table 2 summarizes ongoing clinical trials with giredestrant (GDC-9545) for the treatment of early or advanced hormonal receptor-positive BC. In addition, giredestrant (GDC-9545) is also being studied in the treatment of ER-positive/HER2-positive BC.

Table 2. Ongoing clinical trials with giredestrant (GDC-9545) in BC.

Clinical Trial	Phase	Study
NCT03916744	I	A Phase I, Multicenter, Open-Label Preoperative, Short-Term Window Study of GDC-9545 in Postmenopausal Women With Stage I-III Operable, Estrogen Receptor-Positive Breast Cancer
NCT03332797	Ib/II	Multicenter, Open-Label, Dose Escalation, Dose Expansion Study Evaluating the Safety, Pharmacokinetics, and Activity of GDC-9545 Alone or in Combination With Palbociclib and/or LHRH Agonist in Patients With Locally Advanced or Metastatic Estrogen Receptor-Positive Breast Cancer
NCT04802759	Ib/II	Open-Label, Multicenter, Randomized Umbrella Study Evaluating the Efficacy and Safety of Multiple Treatment Combinations in Patients With Breast Cancer (MORPHEUS-Breast Cancer)

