8.4 Primary efficacy endpoint

The change in tumor cell proliferation as measured by Ki67 expression between baseline and the post-treatment tumor biopsy samples by central assessment.

The primary analysis will be done for the mITT analysis set. We only will analyse observed valid cases (observed-cases method).

The global null hypothesis is that the giredestrant (GDC-9545) does not differ from tamoxifen treatment group in the mean percentage of absolute difference in Ki67 between baseline score and after the treatment. The alternative hypothesis is that the giredestrant (GDC-9545) differs from the tamoxifen treatment group.

The test of the null hypothesis is based on a two-sided Wilcoxon unpaired test set at 0.05 alpha level. It includes treatment as a factor. The response variable is the absolute difference in Ki67 score after the treatment. We propose declaring the superiority of giredestrant (GDC-9545) therapy if shown to be superior in this analysis.

We will estimate the 95% confidence intervals (CI) for the mean and median of absolute difference between baseline and the post treatment evaluation in each study arm. The 95% confidence intervals (CI) for the mean and median difference between treatments are estimated by the T-Test and Hodges–Lehmann estimator, respectively.

Individual baseline and post-treatment Ki67 scores will be summarized with dot plots linking with a line the observations of the same patient. Absolute and relative change between baseline and post-treatment will be summarized with waterfall and bar plots.

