4.4.1 Primary Efficacy Endpoint

The change in tumor cell proliferation as measured by Ki67 expression between baseline and the post-treatment tumor biopsy samples by central assessment.

The primary analysis will be done for the mITT analysis set. We only will analyse observed valid cases (observed-cases method).

The global null hypothesis is that the giredestrant (GDC-9545) does not differ from tamoxifen treatment group in the mean percentage of absolute difference in Ki67 between baseline score and after the treatment. The alternative hypothesis is that the giredestrant (GDC-9545) differs from the tamoxifent treatment group.

The test of the null hypothesis is based on a two-sided Wilcoxon unpaired test set at 0.05 alpha level. It includes treatment as a factor. The response variable is the absolute difference in Ki67 score after the treatment. We propose declaring the superiority of giredestrant (GDC-9545) therapy if shown to be superior in this analysis.

We will estimate the 95% confidence intervals (CI) for the mean and median of absolute difference between baseline and the post treatment evaluation in each study arm. The 95% confidence intervals (CI) for the mean and median difference between treatments are estimated by the T-Test and Hodges–Lehmann estimator, respectively.

Individual baseline and post-treatment Ki67 scores will be summarized with dot plots linking with a line the observations of the same patient. Absolute and relative change between baseline and post-treatment will be summarized with waterfall and bar plots.

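### The 80% power was worked out for relative Ki67 reductions, but the primary test compares absolute point changes, and its own power is not stated.

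*Protocol*

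**What the plan says.** **Sizing.** Protocol 8.2 and SAP 1.6 carry the same text. The opening sentence says that absolute changes in Ki67 will be compared. The planning values follow: "We assumed a 70% mean in giredestrant (GDC-9545) Arm vs. 50% mean in tamoxifen with a 29% common standard deviation". The reference calculation is a "two-sided t-test set at 0.05 alpha level", with the result "We planned 34 patients per arm to attain an 80% power". The number is then raised for the non-parametric test, on the ground that "asymptotic efficiency of Wilcoxon test relative to the t-test, never falls below 0.86", and for 10% dropout, to 46 per arm (92 in total).

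**Primary analysis.** Protocol 8.4 states: "The response variable is the absolute difference in Ki67 score after the treatment". The test is a two-sided unpaired Wilcoxon at 0.05 in the mITT set, with treatment as the only factor. SAP 4.4.1 repeats this. The null hypothesis there is that giredestrant does not differ from the "tamoxifen treatment group in the mean percentage of absolute difference in Ki67 between baseline score and after the treatment".

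**Other analyses.** In the table of planned analyses (Protocol Table 6, SAP Table 1), percentage change from baseline is IDs 7-9. These give confidence intervals within each arm and no comparison between arms. The baseline-adjusted regression with Box-Cox transformation is IDs 4-6 and is supportive.

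**The cited study.** Protocol 1.4 reports it as percentage decreases: anastrozole "significantly decreases Ki67 expression (76% and 82%, respectively) compared to tamoxifen alone (59% and 62%, respectively". Table 1 of the protocol lists it under a percentage-decrease column.

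**The concern.** A mean absolute fall of 70 points would need a mean baseline Ki67 of at least 70%, in a population whose only stated limit is a floor of 10%. The planning values must therefore be relative reductions, although the text does not say so.

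Absolute change is a different quantity. A tumour that starts at 12% cannot fall by more than 12 points; one that starts at 50% can fall by 40. Differences in starting value between patients enter the variance of the absolute change, and a test without a baseline term does not remove them. The 0.86 factor allows for using a Wilcoxon test in place of a t-test on the same variable. It does not allow for a change of variable.

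Superiority is declared on this one test. If its power is well below 80%, a drug with exactly the assumed benefit may fail to show it, and readers of the plan would not know that the risk had been taken. The wording of the null hypothesis, which combines a percentage with an absolute difference, leaves unclear which quantity is meant.

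**Working it through.** **1. Reproduce the plan's figure.** Inputs from Protocol 8.2: means 70 and 50, SD 29, two-sided alpha 0.05, power 80%.

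- Standardised effect: d = 20/29 = 0.690.
- Two-sample t-test (noncentral t): n = 33.99, so 34 per arm, with power 80.0%. This agrees with the plan.
- Wilcoxon allowance: 34/0.86 = 39.5, so 40. Dropout: 40/0.90 = 44.4, so 45. The plan says 46, which is close enough.
- Evaluable at 46 per arm less 10%: 46 × 0.90 = 41.4, so 41. This takes the 10% to cover every exclusion from the mITT set.

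The arithmetic is sound for a relative-scale contrast.

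**2. Move to the absolute scale.** Let baseline Ki67 have mean μ and coefficient of variation CV. Let the relative fall have mean m (0.70 or 0.50) and SD 0.29. Two assumptions are mine: the CV, which the documents do not give, and independence of the relative fall from baseline. The absolute fall is baseline × relative fall, so:

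- difference between arms = 0.20 μ
- variance in an arm = μ² × [(1 + CV²)(0.29² + m²) − m²]

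Example at CV = 0.3. Giredestrant: 1.09 × 0.5741 − 0.49 = 0.1358. Tamoxifen: 1.09 × 0.3341 − 0.25 = 0.1142. The mean is 0.1250 and its square root 0.3535, so d = 0.20/0.3535 = 0.566. The mean baseline μ cancels; only the CV matters.

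| Baseline CV | d, absolute scale | t-test power, 41 per arm | Evaluable per arm for 80% (t-test) |
|---|---|---|---|
| 0 | 0.690 | 87% | 34 |
| 0.2 | 0.625 | 80% | 42 |
| 0.3 | 0.566 | 72% | 51 |
| 0.4 | 0.505 | 62% | 63 |
| 0.5 | 0.450 | 52% | 79 |
| 0.6 | 0.402 | 44% | 99 |

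**3. Simulate the planned Wilcoxon.** Settings: 41 per arm, baseline log-normal truncated to 10-95%, beta-distributed relative fall with means 70% and 50% and SD 29%, and 3,000 trials per row.

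| Baseline CV | Wilcoxon, absolute change | Wilcoxon, relative change | Baseline-adjusted log model |
|---|---|---|---|
| 0.15 | 83% | 90% | 94% |
| 0.20 | 79% | 90% | 94% |
| 0.30 | 72% | 89% | 93% |
| 0.35 | 71% | 90% | 94% |
| 0.48 | 61-63% | 90-91% | 93-94% |
| 0.54 | 58% | 89% | 93% |

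The shape of the response matters somewhat. Gamma and log-normal shapes with the same means and SD bring the range for the absolute-change Wilcoxon to 72-82% at CV 0.30 and 59-66% at CV about 0.48. With no baseline spread it is 90-99%. Tested on relative change, the same data give 89-99%.

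**4. Is the powered quantity tested elsewhere?** No. IDs 7-9 report arithmetic and geometric means within each arm. The secondary analyses (Protocol 8.7, SAP 4.4.2) give summary statistics for relative change, but name no between-arm test of it.

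**The case against.** Several points on the other side stand.

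- The primary test is valid. Under randomisation the Wilcoxon keeps its type I error, and chance baseline imbalance is within that error rate. Baseline-adjusted analyses are prespecified as support.
- Absolute change is named consistently as the primary scale. It is a legitimate choice, if a less efficient one.
- The plan attaches 80% to a t-test at 34 per arm. It never states 80% for the final Wilcoxon at 46; the reader is left to infer it.
- A mean fall of 70 points is implausible but not strictly impossible, because eligibility sets no upper limit. Reading 70/50/29 as relative is an inference, though a firm one.
- The size of the loss rests on a baseline spread that no section gives. At a CV of about 0.2 or less the design still reaches about 80%.

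A reader might go further in three ways that the documents do not support.

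- **A fixed power in the range 55-67%.** This depends wholly on the assumed baseline spread and cannot be written in as fact.
- **A misreported source: 76% vs 59%, a gap of 17 and not 20.** Those figures are anastrozole against tamoxifen in postmenopausal women. The protocol's own giredestrant figures are 76-80% (Protocol 1.5.1); against 59% the gap is 17-21, which includes 20. The citation may also support only the SD.
- **The coopERA subgroups show that the absolute scale hides the benefit in low-baseline tumours.** At baseline Ki67 of 20% or more the protocol reports "giredestrant (GDC-9545): 83% reduction; anastrozole: 71"%; below 20% it reports 65% vs 24%. These are preliminary data against anastrozole in postmenopausal women. At illustrative baselines of 15% and 30%, the gaps are 0.41 × 15 = 6.2 and 0.12 × 30 = 3.6 points, so the low-baseline gap is the larger one even in points. The figures do show that independence of relative fall and baseline is only an assumption.

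**Conclusion.** The point holds as a mismatch of scale. The calculation behind 34 and 46 per arm is correct for relative reductions, but the primary test is on absolute points and the plan gives no power for it. Given a 70/50/29 relative fall independent of baseline and 41 evaluable per arm, power is about 80% at a baseline CV near 0.2 (higher below that), about 70-82% near 0.3, and about 57-66% at 0.45-0.55. At that last spread the chance of missing the assumed benefit is about 34-43%, where the plan implies 20%. At every non-zero baseline spread examined, the absolute-change Wilcoxon had less power than an analysis of the same data on the relative scale; where the baseline-adjusted log model was also run, it too had more. The direction of the loss is therefore clear under these assumptions. Its size, and whether power falls below 80%, cannot be settled from the documents.

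**What to change.** **In Protocol 8.2 and SAP 1.6:** say that 70%, 50% and 29% are relative reductions. State an assumed distribution of baseline central Ki67. Give the power of the absolute-change Wilcoxon as a range conditional on that distribution, in place of an implied 80%.

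**In Protocol 8.4 and SAP 4.4.1:** rewrite the null hypothesis on the single scale that is tested.

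**In IDs 7-9:** add a between-arm estimate of relative change with a 95% confidence interval.

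**Optional.** Make the baseline-adjusted model (ID 4) primary, with its transformation fixed in advance; at present it is Box-Cox, with the power left open. This is defensible only if it can be documented that nobody has reviewed central Ki67 by arm. The trial is open-label, and Protocol 8.11 has the Steering Committee, which includes site investigators, evaluating efficacy data every 6 months. The change would need a dated rationale in SAP section 6, which now records none. If this condition cannot be met, keep the planned primary test and make only the changes above.

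**Cost.** Wording in both documents and one added output, with no more patients or data. The price is a stated power that may look less favourable. The optional route adds the credibility risk of changing the primary test late.

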8.3 Populations for Analyses

Modified intention to treat (mITT) set

All randomly assigned patients that accomplish major selection criteria (Central Ki67 $\geq 10\%$), with ≥ 14 days of treatment*, and the central Ki67 evaluated at baseline and at most on the day after the completion of treatment Subjects will be analyzed according to treatment allocated. The mITT set will be used for primary and secondary efficacy analysis.

* One day of deviation from the 15 days of treatment indicated for the main objective will be accepted.

Intention-to-treat (ITT) analysis set

All patients randomized. Subjects will be analyzed according to treatment allocated. The ITT set will be used for supportive efficacy analyses.

Per protocol analysis (PP) set

All randomly assigned patients that accomplish major selection criteria, with Ki67 evaluable values at baseline and after the treatment, with a minimum exposure to the drugs assigned in the randomized arm, and without major protocol deviations. Criteria for determining the "per protocol"

group assignment would be established by the Steering Committee before the statistical analysis begins. Subjects will be analyzed according to treatment received. The PP set will be used for supportive efficacy analyses. This analysis will only occur if this set differs by $\geq 10\%$ from the mITT set.

Safety analysis set

Includes all patients who received at least one dose of the study drug. Subjects will be analyzed according to treatment received. The safety set will be used for analyses of safety endpoints.

[REDACTED]

[REDACTED]

